#### Attachments

## Data Collection & Research Materials

In this section, please provide the following:

- Describe all sources or methods for obtaining research materials about or from living individuals (such as specimens, records, surveys, interviews, participant observation, etc.), and explain why this information is needed to conduct the study.
- For each source or method described, please list or attach all data to be collected (such as genetic information, interview scripts, survey tools, data collection forms for existing data, etc.).
- If you will conduct a record or chart review, list the beginning and end dates of the records you will view.

Screening-related questions include:

- 1) Are you (or the patient if LAR) receiving dialysis regularly?
- 2) Do you (or the patient if LAR) an underlying muscle disorder such as paralysis, neuromuscular disorder, or myopathy?
- 3) Have you (or the patient if LAR) been diagnosed with cirrhosis?
- 4) Have you (or the patient if LAR) been treated for a cancer of any kind within the past year?

What RRT subjects will be asked to do/what happens in the study (in sequential order)

- Blood and effluent will be collected at the start of CRRT, at 48 hours, and on day 7 or ICU discharge, whichever comes first. The blood draw for research is 5 mL per draw.
- At hospital discharge, the patient will undergo a series of muscle strength and function tests including 1)Medical Research Council sum score (MRC-ss), a measure of global peripheral muscle strength that is the current clinical standard for diagnosing ICU-AW, 2) Maximal isometric knee extensor and dorsiflexion muscle strength measured as peak force production and rate of force development, and 3) Maximal isometric grip strength. Muscle power will be measured by the repetitive 5x sit-to stand test a reliable and validate measure of lower-extremity power. Physical function and frailty will be measured using 1) the Short Performance Physical Battery (SPPB), 2) six-minute walk test (6MWT), and 3) Clinical Frailty Scale. SPPB is a performance-based composite test with a total of 12 points including components of balance, chair to stand test, and 4-meter habitual gait speed.

Variables collected from the patient's chart for case subjects will include:

- Demographic data (Age, Gender, Race, BMI)
- SOFA or APACHE score at initiation
- Comorbidities (Charlson Score)
- Cause of AKI (Sepsis, post-surgical, etc.)
- Location of ICU (medical vs surgical)
- Laboratory data at baseline (BMP, CBC, lactate, albumin, INR)
- Daily laboratory data
- % Volume overload at initiation and daily
- CRRT variables (BFR, dose, therapy fluid flow rate, UF, filtration fraction).
- Reason for filter loss
- Time to death (censored for patient drop out or loss to follow up)
- In-hospital Mortality
- Time to renal recovery (censored for interfering events)
- Renal Recovery at hospital discharge

What Control subjects will be asked to do/what happens in the study (in sequential order)

- At hospital discharge, the patient will undergo a series of muscle strength and function tests including 1) Medical Research Council sum score (MRC-ss), a measure of global peripheral muscle strength that is the current clinical standard for diagnosing ICU-AW, 2) Maximal isometric knee extensor and dorsiflexion muscle strength measured as peak force production and rate of force development, and 3) Maximal isometric grip strength. Muscle power will be measured by the repetitive 5x sit-to stand test a reliable and validate measure of lower-extremity power. Physical function and frailty will be measured using 1) the Short Performance Physical Battery (SPPB), 2) six-minute walk test (6MWT), and 3) Clinical Frailty Scale. SPPB is a performance-based composite test with a total of 12 points including components of balance, chair to stand test, and 4-meter habitual gait speed.

Variables collected from the patient's chart for control subjects will include:

- Demographic data (Age, Gender, Race, BMI)
- SOFA or APACHE score at ICU admission
- Comorbidities (Charlson Score)
- Cause of respiratory failure (COPD, PNA, etc.)
- Location of ICU (medical vs surgical)
- Laboratory data at baseline (BMP, CBC, lactate, albumin, INR)
- Daily laboratory data

#### Attachments

### Resources

Describe the availability of the resources and adequacy of the facilities that you will use to perform the research. Such resources may include:

- Staffing and personnel, in terms of availability, number, expertise, and experience;
- Computer or other technological resources, mobile or otherwise, required or created during the conduct of the research;
- Psychological, social, or medical services, including equipment needed to protect subjects, medical monitoring, ancillary care, or counseling or social support services that may be required because of research participation;
- Resources for communication with subjects, such as language translation/interpretation services.

The research procedures will be carried out at the University of Kentucky Medical Center, as well as at the University of Iowa and University of New Mexico. The participants will be followed at the University of Kentucky by [name] and his research team which includes: physicians, certified nurses, and clinical research coordinator during the study period, while activities at Iowa will be supervised by [name]; activities at the University of New Mexico will be supervised by [name] [name].

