
## Objectives

List your research objectives. Please include a summary of intended research objectives in the box below.

Aim 1: Determine the rate and degree muscle wasting in critically ill patients with AKI-RRT vs historic ICU controls without AKI during ICU stay. Hypothesis 1: Patients with AKI-RRT have faster decline in rectus femoris and tibialis anterior muscle size compared to controls .

Aim 2: Determine the trajectory of muscle recovery in patients following an episode of AKI-RRT compared to matched controls by measuring muscle mass, muscle strength and power, and functional status in patients at discharge and at 1 and 3 months thereafter. Hypothesis 2: Patients with AKI-RRT will have a slower trajectory of muscle recovery following ICU discharge compared to matched patients without AKI.

Aim 3: Use trend analysis to determine that changes in plasma amino acid levels on RRT correlate with lean muscle loss during AKI-RRT and predict lack of muscle recovery at 1 and 3 months. Hypothesis 3: Trends in amino acid levels during treatment with RRT will correlate with MKUS determinations of lean body mass in the short-term and will predict lack of muscle recovery at 1 and 3 months.

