This is a prospective, non-blinded, non-randomized study to assess the impact of CRRT on critical illness muscle wasting. As the study is observational and non-interventional in nature, there will be no placebo administered in the course of the study. Patients will be identified based on conversations with ICU and Nephrology consult teams (in addition to chart screening) to determine which patients are likely to receive RRT therapy due to AKI and critical illness. In the first aim, patients will undergo musculoskeletal ultrasound (MKUS) assessments within 24 hours of CRRT initiation, and again at 48 hours and 168 hours. In addition, blood will be drawn at these timepoints and stored for later analysis. In Aim 2, the trajectory of muscle mass recovery will be determined through visits at the time of hospital discharge (to be completed within the hospital), and then at 1 and 3 months thereafter, which will entail separate visits. At these sessions, patients with AKI-RRT and matched controls will undergo measurements of muscle mass, strength, and function at hospital discharge and at 1- and 3-months following discharge. Measurements will include MKUS to determine CSA and muscle echogenicity in the RF and TA muscles. We will evaluate muscle strength by measuring: 1) Medical Research Council sum score (MRC-ss), a measure of global peripheral muscle strength that is the current clinical standard for diagnosing ICU-AW34, 2) Maximal isometric knee extensor and dorsiflexion muscle strength measured as peak force production and rate of force development38, and 3) Maximal isometric grip strength 40. Muscle power will be measured by the repetitive 5x sit-to stand test a reliable and validate measure of lower-extremity power. Physical function and frailty will be measured using 1) the Short Performance Physical Battery (SPPB), 2) six-minute walk test (6MWT), and 3) Clinical Frailty Scale. SPPB is a performance-based composite test with a total of 12 points including components of balance, chair to stand test, and 4-meter habitual gait speed. The 6-MWT assesses the distance a subject can walk in six minutes providing a global marker of physical function and representation of cardiopulmonary endurance. We will summarize descriptive statistics at each timepoint including mean and standard deviation or median and interquartile range, as appropriate. Independent t-tests and Mann-Whitney U tests for non-parametric data will be used as appropriate to compare differences in the testing outcomes between cases and controls at each timepoint. Two-way repeated measures ANOVA will be performed to assess the within change in muscle metrics over time and between group comparisons to understand the trajectories of muscle recovery.

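### Controls are not tied to the case's site and the named tests pool three sites and ignore the matching, so site, scanner and care differences can enter the Aim 2 contrasts if the site mix differs

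*Protocol*

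**What the plan says.** Resources in the protocol states that the procedures "will be carried out at the University of Kentucky Medical Center, as well as at the University of Iowa and University of New Mexico". New Mexico joined through the modification described in this same form.

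Objectives defines two comparator groups. Aim 1 compares "critically ill patients with AKI-RRT vs historic ICU controls without AKI during ICU stay". Aim 2 follows recovery "compared to matched controls by measuring muscle mass, muscle strength and power, and functional status". The site, period, scanner and operators of the historic controls are not given, and no matching variable is named for Aim 2.

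Study Design describes the study as non-randomised. On the Aim 2 visits it says "Measurements will include MKUS to determine CSA and muscle echogenicity in the RF and TA muscles". It then names independent t-tests or Mann-Whitney tests "to compare differences in the testing outcomes between cases and controls at each timepoint", and adds: "Two-way repeated measures ANOVA will be performed to assess the within change in muscle metrics over time and between group comparisons". Neither analysis has a site term or uses the matching. The chart-variable lists in Research Procedures and in Data Collection & Research Materials include ICU type (medical or surgical) but neither site nor scanner.

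**The concern.** Without randomisation, nothing balances site between cases and controls except the rule for choosing controls, and the protocol states no such rule. Echogenicity is image brightness, so it can shift with scanner and preset. CSA can shift with local measurement practice. Nutrition, mobilisation and discharge practice can also differ between hospitals. If one site supplies a larger share of the cases than of the controls, any of these differences appears as a difference between AKI-RRT patients and controls.

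A pooled unpaired test cannot separate the two. An analysis plan can add a site term later, but it cannot create same-site controls that were never enrolled. That is why the way controls are selected matters more here than the missing term. The named unpaired tests also make no use of the matching that Objectives promises.

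**Working it through.** The protocol states no effect size, SD, significance level, power, case-to-control split or site split, only a maximum of 60 subjects (Project Information). There is therefore no planned figure to reproduce, and every size below rests on assumptions.

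**1. Bias of a pooled contrast.** Let p_j and q_j be the shares of cases and controls from site j, and s_j the site's offset in SD units. Then

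bias = Σ (p_j − q_j) × s_j.

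For one offset site this is offset × difference in share:

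| Offset (assumed) | 20 points | 33 points | 50 points |
|---|---|---|---|
| 0.25 SD | 0.05 | 0.08 | 0.13 |
| 0.5 SD | 0.10 | 0.17 | 0.25 |
| 1.0 SD | 0.20 | 0.33 | 0.50 |

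The range is 0.05 to 0.50 SD. If p_j = q_j at every site, the bias is zero whatever the offsets.

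**2. Type I error of the pooled t-test.** Simulation with 20,000 runs and no true group effect. Assumptions: two-sided 5% level, 30 cases and 30 controls, cases spread evenly over three sites, two sites offset from the third by d.

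| Control source | d = 0.2: bias; error | d = 0.5: bias; error | d = 0.8: bias; error |
|---|---|---|---|
| Same mix as cases | 0; 4.8% | 0; 4.6% | 0; 3.6% |
| Two thirds from one site | 0.07; 5.6% | 0.17; 8.7% | 0.27; 14.1% |
| All from one site | 0.13; 7.9% | 0.33; 24.3% | 0.53; 50.3% |

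The biases agree with the formula. In the last row they are 2/3 × d. In the middle row they are (2/3 − 1/3) × d. With 15 per group and all controls from one site, the error is 5.9%, 13.8% and 26.7%. A model with site as a fixed effect holds about 5% in every scenario.

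**3. Cost of pooling when the mix is equal.** With a third of patients at each site and offsets 0, d, d, the between-site variance is (2/9)d². The pooled SD is then √(1 + (2/9)d²), which is 1.004, 1.027 and 1.069 for d = 0.2, 0.5 and 0.8. This is a loss of precision and not a bias.

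**4. What cancels.** Write a measurement as patient level + s_j + change over time. In a within-patient difference s_j drops out, provided both scans come from the same scanner and preset. It therefore drops out of the decline in Hypothesis 1 and of the group-by-time term in Aim 2. It stays in full in a comparison of absolute values at one visit. If the change itself varies by site because care varies, with site-specific change c_j, the contrast of changes carries Σ (p_j − q_j) × c_j, which does not cancel.

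**5. Limits of adjustment.** If all controls come from one site, a site-adjusted model compares only that site's 10 cases with the 30 controls. Its standard error is √(1/10 + 1/30) = 0.365 SD, against √(1/30 + 1/30) = 0.258 SD with 30 against 30. That is a rise of about 41%.

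**The case against.** The strongest reply is that bias needs a difference in site mix, and the protocol states none. Resources places the procedures as a whole at all three sites, and these include the control visits at discharge and at 1 and 3 months. The natural reading of Aim 2 is that each site follows its own cases and controls. A reader might infer from the silence that site differences do distort the comparison. The document does not support that; it only leaves the possibility open.

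A reader might also take Aim 1 as the most exposed aim because its controls are historic. Its hypothesis, however, concerns decline within patients, where a constant scanner offset cancels. Echogenicity appears under the Aim 2 visits, and the named tests follow the Aim 2 description. For Aim 1, what remains is unequal care, changes over time, and patients scanned on more than one machine.

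The form asks only for summaries, lists a separate protocol file, and may be backed by an analysis plan. A missing site term alone would therefore be no finding. Background reports good inter-rater reliability, and the strength and walking tests involve no scanner.

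These points limit the concern but do not remove it. Study Design itself names the tests, and names unpaired ones for a matched comparison. It plans comparisons of absolute values at each visit, where offsets stay. No passage keeps a patient on one scanner as follow-up moves from the hospital to outpatient visits. Reliability between raters does not address differences between scanners or sites.

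**Conclusion.** The concern holds in a conditional form. Controls are not tied to site, and the stated tests pool sites and ignore the matching. Site, scanner and care differences can therefore enter the contrast if the site mix differs between groups. The main exposure is the by-timepoint Aim 2 comparison of absolute CSA and echogenicity. Site differences in care can also reach the trajectory comparisons.

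The protocol does not show that any bias exists, and its size is unknown. The range of 0.05 to 0.50 SD depends entirely on the assumed offsets and imbalances and runs from negligible to large. With equal mix the harm is a small loss of precision. The change is still worth making before further enrolment, because it costs little and selection of controls cannot be repaired at analysis.

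**What to change.** For Aim 2:

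- Select each control from the same site as its case, and name the other matching variables.
- Replace the pooled unpaired tests with a model that has site as a fixed effect and accounts for the matched sets, for example by a random effect for the set. Same-site selection also balances differences in care, which a site main effect alone does not remove from the group-by-time term.
- Keep each patient on one scanner and preset throughout, and record site and scanner in the dataset.

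For Aim 1:

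- State the site, period and scanner of the historic controls.
- Analyse within-patient change.
- Report a comparison restricted to same-site controls as a sensitivity analysis, without excluding sites from the main contrast.

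Two stricter rules are not advised. Dropping sites without historic controls from the main Aim 1 contrast could raise the standard error from 0.258 to 0.365 SD on the assumptions above. Reporting echogenicity only as change would remove a planned comparison at discharge.

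The cost is a smaller matching pool at each site, two degrees of freedom for site, and some revised wording.

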### Potential Risks & Benefits

#### Risks

- Describe any potential risks – including physical, psychological, social, legal, ability to re-identify subjects, or other risks. Assess the seriousness and likelihood of each risk.
- Which risks may affect a subject's willingness to participate in the study?
- Describe likely adverse effects of drugs, biologics, devices or procedures participants may encounter while in the study.
- *Qualitative research* - describe ethical issues that could arise while conducting research in the field and strategies you may use to handle those situations.
- Describe any steps to mitigate these risks.

#### Benefits

- Describe potential direct benefits to study participants – including diagnostic or therapeutic, physical, psychological or emotional, learning benefits. This cannot include incentives or payments.
- State if there are no direct benefits.
- Describe potential benefits to society and/or general knowledge to be gained.

Describe why potential benefits are reasonable in relation to potential risks. If applicable, justify why risks to vulnerable subjects are reasonable to potential benefits.

Risk of blood draw will be minimized by drawing from RRT circuit once RRT is initiated. Accessing the dialysis circuit or arterial line for obtaining the research blood samples may increase the risk of infection. However, we will try as much as possible to combine these draws with labs that will be drawn anyway as part of routine RRT care, so additional risk should be minimal. Because ultrasound is a non-invasive imaging modality, risks of ultrasound are minimal. The risks of injury during assessment of muscle strength and function is minimal. There is a risk of loss of confidentiality, which we will minimize by using REDCap for data storage, and by removing identifying data as soon as the project is completed and published.

There are no direct benefits to the patient. The findings will not be communicated to the primary team, and will not be used to inform the patient's care in any way. With regards to society and general knowledge, AKI-RRT is a procedure with a very high rate of mortality (>50%). Patients who develop muscle loss after AKI-RRT initiation are at even further risk of morbidity and mortality. If AKI-RRT is shown to precipitate muscle loss due to amino acid removal, with slower rates of muscle recovery, this information can be used in future trials to study interventions such as the addition of amino acids to the dialysate/replacement fluid or early initiation of physical therapy/mobilization while on CRRT that would decrease sarcopenia development in this susceptible patient population, in order to

improve patient-centered outcomes.

## Available Alternative Opportunities/Treatments

Describe alternative treatments or opportunities that might be available to those who choose not to participate in the study, and which offer the subject equal or greater advantages. If applicable, this should include a discussion of the current standard of care treatment(s).

N/A

[Back to Top](#)

## Records, Privacy, and Confidentiality

Specify where the data and/or specimens will be stored and how the researcher will ensure the privacy and confidentiality of both. Specify who will have access to the data/specimens and why they need access.

Describe how data will be managed after the study is complete:

- If data/specimens will be maintained, specify whether identifiers will be removed from the maintained information/material.
- If identifiers will not be removed, provide justification for retaining them and describe how you will protect confidentiality.
- If the data/specimens will be destroyed, verify that this will not violate [retention policies](#) and will adhere to applicable facility requirements.

If this study will use de-identified data from another source, describe what measures will be taken to ensure that subject identifiers are not given to the investigator.

If applicable, describe procedures for sharing data/specimens with collaborators not affiliated with UK.

For additional considerations:

[Return of Research Results or Incidental Research Findings](#)

[HIPAA policies](#)

[FERPA policies](#)

[Procedures for Transfer agreements](#)

[Information regarding multi-site studies](#)

[NIH Genomic Data Sharing \(GDS\) Policy](#)

[Digital Data](#)

Research materials will include biologic samples, ultrasound imaging, paper/hard copy records, and electronic records. Biologic samples will be taken in the form of blood draws and effluent collection. These samples are necessary for the assessment of amino acid loss in patients with AKI-RRT. Ultrasound imaging is necessary for the assessment of muscle loss in patients in an ICU setting. Hard copy/electronic records are necessary for the screening and enrollment process.

Biologic samples - We will use a coding system rather than directly identifying information on the specimens. The code will be stored in REDCap. Samples will be stored in a secure lab space.

Paper/hard copy records - After signed consent is obtained, a copy will be made and given to the patient or LAR. The original consent documents will be given to the PI, and kept in a secure location that will be locked when not in use. Paper records, where applicable, will be stored at [name]. This room is locked at all times when unoccupied.

Electronic records - REDCap will be used for data storage. REDCap is a University-supported, server-based program designed to securely store data. It is password protected, and will be de-identified if downloaded.

This will be a multi-site study, but no materials, other than de-identified data, will be shared between sites. Furthermore, these sites will be added via a modification request once IRB approval has been obtained.

Risk of blood draw will be minimized by drawing from the CRRT circuit once CRRT is initiated or from a central line. Tests of muscle strength and function will be performed by appropriately trained research team members. There is a risk of loss of confidentiality, which we will minimize by using REDCap for data storage, and by removing identifying data as soon as the project is completed and published.

**UK IRB policies state that IRB-related research records must be retained for a minimum of 6 years after study closure. Do you confirm that you will retain all IRB-related records for a minimum of 6 years after study closure?**

Yes  No

[Back to Top](#)

